- **5.C.2. Notification of the MSU team.** Once the MSU team notifies the dispatch center that they are on-call, 911 calls are screened for stroke symptoms by EMS dispatchers. Both the dispatchers and their supervisors have been trained in stroke symptoms by the MSU Team. Training includes an instructional DVD reviewing stroke symptoms and loaded onto their computers, and a printed algorithm of questions to be asked if stroke is suspected. Currently, all calls are immediately triaged by the dispatcher onto one of 44 diagnostic pathways such as "fall", "chest pain", "gunshot", etc. Only one of these pathways is "stroke". After listening to the initial history, the dispatcher immediately dispatches the nearest available Emergency Medical Technician (EMT) or Paramedic team depending on proximity of available units and severity level of the pathway. After EMT/paramedic dispatch, the MSU team is activated by one of four pathways (see Criteria 1, in Section 4 above). 1). If the caller mentions the word "stroke", the call is triaged onto the "stroke" pathway and if the patients is within the catchment area of the MSU (see below), the dispatcher also immediately dispatches the MSU team using a dedicated beeper and cell phone line. 2). If the patient is triaged on one of the non-stroke pathways and the MSU team is not alerted by the dispatch center, but the EMT or paramedic arrives on the scene, discovers that the patient may have had a stroke, and that one of the designated CSCs is a possible transport option, they call back to the dispatch center and ask for MSU team dispatch. All EMTs and paramedics operating within the catchment area of the MSU have been trained in stroke recognition and the need to ask for MSU team dispatch. 3). The MSU team monitors all communication between dispatch and EMS units, and if a possible stroke patient is identified, the MSU team contacts the EMS unit and ask to be "added on" to the call if one of the designated CSCs is a possible transport option. 4). All EMS units transporting stroke patients call the base station for instructions and hospital pre-notification. The base station alerts the MSU team for all transported stroke patients. This serves as a "back up" to methods 1-3. If the MSU team is notified by any of these 4 pathways for a possible stroke and the patient meets Inclusion Criteria as in section 4.1.b.i-iv, the MSU team is deployed. Depending on MSU or SM week, or location of the emergency call in the case of dual MSU/SM locations, either the MSU is dispatched, or the SM pathway, which already has been initiated, is continued.

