- **5.C.3. Mobile Stroke Unit process:** The MSU is staffed by an off-duty Houston Fire Department paramedic, certified CT technician, Vascular Neurologist (VN faculty or fellow) and research nurse (RN). In some cases, the VN is not on board and manages the case remotely via TM; in these cases, the MSU team alerts the on-call TM VN who immediately connects to the mobile TM device on the MSU. Once alerted, the MSU is driven by the paramedic with the VN riding "shotgun" and helping to navigate, while the CT tech and RN ride in the back.

The MSU is stationed in the driveway of the UT-Professional Building (UTPB) which houses the MSU team offices on the 14th floor. There is an elevator outside the MSU team office door leading to the outside door opening onto the designated MSU parking spot. The UTPB is in the heart of the Texas Medical Center (TMC), and surrounded by the 3 CSCs which are the destination of all MSU transports. Currently, direct dispatches of the MSU by EMS are limited to a 5-8 mile radius of the MSU office. We have found that this radius "catchment area" allows dispatch and arrival of the MSU at the emergency site during the time EMS is still on-scene evaluating the patient. Additionally, the MSU is alerted to patients from outside the catchment area by pathways # 2 or 3 in section 6b. Under any of these pathways, if the MSU cannot reach the patient before the EMS unit is ready to depart the scene with the patient, the MSU can arrange to "rendezvous" with the EMS squad en-route. Both the paramedic and RN carry a two-way HFD radio and establish direct radio communication with the EMS team in charge of the patient on site. This enables the MSU team to notify the on-site EMS team that they are en-route, their ETA, and, in some cases, the need to rendezvous. Also, the two way radio allows the on-site EMS squad to "disregard" the MSU if the squad determines that the patient does not have a qualifying stroke.

Once the MSU is activated and assigned to a case, they are considered "out of service" until the call is completed; during this interval they are not activated for any additional stroke alerts.

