- Comparing all patients treated with IAT (separate analyses for those adjudicated as tPA eligible, all tPA treated, or all IAT with or without tPA) on MSU weeks compared to patients on SM weeks.
 - utility-weighted mRS at 90 days
 - ordinal (shift) analysis of mRS at 90 days
 - proportion of patients achieving 90-day mRS 0,1 vs 2-6
 - 30% improvement from baseline to 24hr NIHSS
- The time from LSN to tPA treatment on all patients treated within 4.5 hours of LSN on MSU weeks compared to similarly eligible patients on SM weeks. N.B. Patients will include all enrolled patients actually treated with tPA (or on SM weeks, eligible for tPA treatment) meeting all inclusion and exclusion criteria, and based on the final determination of time of LSN. One analysis will compare the median times. A second analysis will also capture the patients who were eligible but did not receive tPA because it was too late, categorizing time into the following groups (e.g., 0-60min, 61-90min, 91min-180min, 181-270min, eligible but no tmt because>270).
 - Of the enrolled patients that were eligible for treatment with tPA (according to

published guidelines) on MSU weeks compared to SM weeks, the percent that were treated within 4.5 hours and within 60 minutes of LSN.

- The time from LSN, from alarm time, and from ED arrival to start of endovascular procedure (intra-arterial thrombectomy-IAT) in patients who meet pre-specified criteria for IAT on MSU weeks compared to SM weeks. N.B. All patients receiving IAT will be included in this outcome.
- The proportion of all tPA-eligible patient having IAT on MSU weeks compared to SM weeks
- The median/mean time from LSN to tPA therapy decision on all patients considered for treatment within 4.5 hours of LSN on MSU weeks compared to SM weeks. N.B. Patients will include all enrolled patients meeting inclusion criteria whether or not treated with tPA.
- Time between 911 call and onset of etiology-specific BP management on MSU weeks compared to SM weeks. N.B. Patients will include all enrolled patients.

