mRS, age, Black race, gender, and dichotomized time from LSN to EMS/MSU arrival (>1hr versus ≤1hr). Standardized mean differences were used to assess covariate balance before and after weighting (all standardized mean differences were < 0.1). The predicted probabilities were used to calculate stabilized inverse probability weights (IPW). The 90-day uw-mRS was further described using means and standard deviations and by fitting a univariate linear regression with outcome (90-day uw-mRS), covariate MSU group, and IPW according to the propensity score. IPW analyses of all enrolled patients was added post-hoc to assess the chances of post-enrollment selection bias and to align analysis with overall MSU vs EMS management with outcomes discharge mRS and 24hr NIHSS.

Utility weights

The sample size was originally designed using the Dawn trial utility weights that were derived based on a United Kingdom sample and using the 3-level version of EQ5D. EQ5D-5L has been in use for more than a decade. However, the corresponding population-level utility weights for 5L had not been developed for many countries, and most countries only have population-level weights for the much older EQ5D-3L. In 2019 a study was published by Pickard et al. conducted a survey to develop utilities based on a US population and using the 5-level version of EQ5D (EQ5D-5L), which is more relevant to the participants in the BEST-MSU study. Using their Probit model estimated parameters to calculate utilities, in June 2020 we fit a linear regression model with these utilities (using 90-day EQ5D-5L) as the outcome and the 90-day mRS indicator variables as the independent variables to estimate our specific utility-weighted mRS. We also applied both the Dawn and the newly derived utility weights to the B-PROUD data and observed that results were consistent in the comparison of their mobile stroke unit data and their non-mobile stroke unit groups between these two weight choices. These were presented during the June 2020 study monitoring committee and were approved to use as the primary outcome of our trial. The weights based on the June 2020 data are presented in Table.

Table. Comparison of utility weights.

mRS	Dawn weights (previous MSU weights)	ENCHANTED trial weights	New proposed MSU
0	1	0.977	1
1	0.91	0.885	0.91
2	0.76	0.748	0.72
3	0.65	0.576	0.65
4	0.33	0.194	0.18
5	0	-0.174	0.05
6	0	0	0

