5.1.5. Subgroup Analysis

Tests of effects within subgroups will be driven by clinical rationale. To reduce the potential for spurious results, we would test for a sub-group treatment interaction at a 0.2 critical level. Any subgroup analyses that are not pre-specified would be considered post hoc and reported as requiring confirmation in future studies. Estimates of the MSU effect will be obtained separately for pre-specified subgroups with significant treatment-by-subgroup interactions, using the methods described above. Pre-specified subgroups include (1) patients treated via TM versus on-site VN, (2) patients treated at various sites, (3) patients that had the EMS arrive (for SM) or MSU arrive (for MSU) within ≤ 1 hr and those that arrived >1 hr of LSN, and (4) race. For (3), time will also be considered as a continuous variable and the interaction between time and MSU/SM will be assessed with transformations or restricted cubic splines of time used if appropriate).

When doing the TM subgroup analysis, we anticipate that there may be demographic differences between sites that are doing TM versus onboard VN. For this analysis we will conduct regression models, adjusting for baseline NIHSS, age, pre-morbid mRS, time since last seen normal, and previous TIA/stroke, in a linear regression model.

Analyses of post-randomization sub-groups are subject to many biases. Thus any analyses of post-randomization sub-groups, such as those treated with IAT, would be considered on a case by case basis requiring tailored use of advanced statistical methods⁹ and careful interpretation.

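### Subgroup 3 stops its clock at EMS arrival in SM but at MSU arrival in the MSU arm, so its early and late strata are not comparable where the MSU arrives after EMS (minor)

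*SAP*

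**What the plan says.** SAP 5.1.5 lists as its third pre-specified subgroup "patients that had the EMS arrive (for SM) or MSU arrive (for MSU") within one hour of LSN versus later. The same time is also used as a continuous effect modifier, with transformations or splines if needed. Interactions are tested at 0.2, and "Estimates of the MSU effect will be obtained separately for pre-specified subgroups with significant treatment-by-subgroup interactions".

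The post-hoc propensity model in SAP 5.1.2 includes "dichotomized time from LSN to EMS/MSU arrival" at the same one-hour cut, without saying which arrival applies to which arm. It reports "covariate balance before and after weighting (all standardized mean differences were < 0.1").

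On the order of events, Protocol 5.C.2 says: "After EMT/paramedic dispatch, the MSU team is activated by one of four pathways". On stroke-pathway calls "the dispatcher also immediately dispatches the MSU team" as well. Other pathways start when a crew already on scene asks for the MSU, or when a crew is already transporting. Protocol 5.C.3 says the catchment radius "allows dispatch and arrival of the MSU at the emergency site during the time EMS is still on-scene evaluating the patient", and that the MSU otherwise meets EMS en route.

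**The concern.** A subgroup that is to show whether the MSU effect differs between early and late patients needs strata that mean the same thing in both arms. Here they are cut on two different events. An on-scene request, an en-route alert or a rendezvous each puts the MSU after EMS, so stratum membership depends partly on the arm. In the MSU arm the stratifier also depends on MSU dispatch and travel, so it is not a pure baseline variable.

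At stake are the two stratum-specific MSU effects and any statement that early patients gain more or less than late ones. If the propensity covariate uses the same arm-specific clock, weighting on it would balance the recorded variable while unbalancing the true time to first contact. The standardized difference on the recorded variable could not show that.

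**Working it through.** The documents give no figure for this subgroup, so there is none to reproduce.

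**Inputs from SAP 4.1.** N = 1038, 5% loss, 3:2 allocation, SD 0.385, target difference 0.07. Evaluable: 1038 × 0.95 = 986, or 592 MSU and 394 SM.

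**Assumptions (not in the documents).** LSN-to-EMS time is log-normal, median 50, 60 or 75 min, log-SD 0.6 or 0.8, cut at 240 min, and identical in both arms. MSU arrival is EMS arrival plus a constant lag L of 5, 10 or 15 min. The adjusted outcome gradient is 0.05 or 0.10 uw-mRS per hour of delay.

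**Mechanism.** In SM, early means EMS time ≤ 60. In the MSU arm it means EMS time ≤ 60 − L. Within each stratum the MSU patients therefore have shorter true EMS times, so both strata lean the same way.

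**One setting in full (median 60, log-SD 0.8, L = 10).**
- SM early share: Φ(0) / Φ(ln 4 / 0.8) = 0.500 / 0.958 = 0.522.
- MSU early share: Φ(ln(50/60) / 0.8) / 0.958 = 0.410 / 0.958 = 0.428.
- Reclassified: 0.522 − 0.428 = 0.094.
- Standardized difference: 0.094 / √[(0.522 × 0.478 + 0.428 × 0.572) / 2] = 0.19.
- Mean true EMS time, SM minus MSU (simulated): 4.4 min early, 9.0 min late. At 0.10 per hour: 4.4/60 × 0.10 = 0.007 and 9.0/60 × 0.10 = 0.015.
- Stratum SE: early 0.385 × √(1/253 + 1/206) = 0.036; late 0.385 × √(1/339 + 1/188) = 0.035. The lean is 0.20 SE early and 0.43 SE late.
- Spurious interaction: 0.015 − 0.007 = 0.008. Its SE is √(0.036² + 0.035²) = 0.050, so it is 0.16 SE, and rejection at the 0.2 level becomes about 0.21.
- Attenuation of true effects 0.10 early and 0.04 late: the late stratum reads 0.04 + 0.06 × 0.094/0.572 = 0.050, so the interaction of 0.060 reads 0.050.

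**All six timing settings:**

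| Constant lag | MSU patients reclassified | Lean, early | Lean, late | Standardized difference | Interaction of 0.060 reads |
|---|---|---|---|---|---|
| 5 min | 4–6% | 0.002–0.005 | 0.003–0.008 | 0.09–0.12 | 0.052–0.056 |
| 10 min | 9–12% | 0.003–0.009 | 0.006–0.016 | 0.19–0.25 | 0.046–0.052 |
| 15 min | 14–19% | 0.005–0.014 | 0.009–0.024 | 0.29–0.39 | 0.040–0.048 |

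The worst late-stratum ratio (15 min, 0.10 per hour) is 0.62 to 0.66 SE. Allowing random lags as well, the spurious dichotomous interaction is at most about 0.4 SE (rejection about 0.23). Bias in a linear continuous-time interaction is 0 for a constant lag and at most 0.008 per hour for a random one. The spline version was not tested.

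**If the MSU sometimes arrives first.** With the MSU first in 20% of calls (mean lag 4.2 or 8.4 min) the lean is 0.001–0.005 early and 0.003–0.017 late. With the MSU first in 40% (mean lag 1.3 or 2.5 min) it is 0.000–0.001 and 0.001–0.008.

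**Separate check on run-in data.** Interpolating the 13 LSN-to-tPA times in Protocol 4.C, with MSU arrival 10 to 28 min before tPA, a 10-minute lag moves about 4% to 13% of MSU patients out of the early stratum. A second simulation with different distributions gave within-stratum differences of about 0 under one clock and about 0.006 to 0.008 at 10 min under the split clock.

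**Propensity model, if it uses the split clock and is weighted on this covariate alone.** In the setting above, the pooled early share is (592 × 0.428 + 394 × 0.522) / 986 = 0.466. The imbalance left in true time is 0.466 × 4.4 + 0.534 × 9.0 = 6.9 min. Over all settings it is 3 to 11 min, or 0.003 to 0.018 uw-mRS.

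**What the reported balance implies.** If the figure below 0.1 also covers the unweighted data and this covariate uses the split clock, a constant lag can be at most 4.3 to 5.6 min. The lean is then at most about 0.004 early and 0.009 late, and the propensity bias at most 0.006.

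**The case against.** The strongest reply concerns weight. The lean is a fraction of a standard error, in estimates produced only after an interaction passes 0.2. SAP 3.3 asks for caution with secondary analyses, and SAP 5.1.5 warns about post-randomization subgroups. Every size above rests on a lag, a time distribution and a gradient that the documents do not state. The simulation also assumes equal time distributions in both arms, although Protocol 7.D and SAP 4.1 report unequal alerting or enrolment. All of this stands and is why the point is minor. General cautions do not, however, repair a definition that differs by arm.

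The propensity part is inference. EMS/MSU arrival could mean whichever comes first, the actual model has six other covariates, and the analysis is openly post hoc. This supports asking for a definition, not asserting a bias.

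Subgroup 3 was added to the SAP in January 2019, and the propensity results are reported in the past tense. A redefinition now is post hoc under SAP 5.1.5's own rule. That also stands, and it is why a common-clock version should be added, not substituted.

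A reader might infer that the primary result is distorted. The documents do not support that: the primary model in SAP 5.1.2 names no arrival time among its covariates. Nor do they show that the MSU always arrives second, since it is also sent at once on stroke-pathway calls.

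**Conclusion.** The concern holds in a limited form. As written, subgroup 3 makes stratum membership depend on arm whenever the MSU arrives after EMS, and the protocol's dispatch sequence makes that order likely for many patients.

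The lean towards MSU is conditional on longer delay predicting worse outcome after adjustment. That is the trial's premise, but no adjusted slope is given. With no gradient and no true interaction the bias is zero. Against the 0.07 target, the largest lean in the range examined is 0.024, in the late stratum at a 15-minute lag. If the reported balance covers unweighted data on the same clock, the ceiling falls to about 0.009.

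Two stronger inferences are not supported. One is that the subgroup would manufacture a significant interaction: the test level hardly changes, and the main distortion is attenuation of a real one. The other is that the propensity analysis is biased: its covariate is undefined, so only a request for clarification is justified. Severity: minor.

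**What to change.** - In SAP 5.1.5, add an analysis of subgroup 3, dichotomous and continuous, on one clock in both arms. Use LSN to first EMS arrival if that was recorded in both. The protocol synopsis lists an on-scene arrival time without saying whose. Otherwise use LSN to 911 call, which the SAP 2.2.2 outcome "Time between 911 call and onset of etiology-specific BP management on MSU weeks compared to SM weeks" already requires in both arms. Do not use alarm time unless it is defined, because three of the four alert pathways can start after the 911 call.
- Base any early-versus-late conclusion on the common-clock version. Report the pre-specified version beside it, and label the common-clock version as added later.
- In SAP 5.1.2, define the arrival covariate and state whether the figure below 0.1 refers to before weighting, after weighting, or both. If the covariate is arm-specific, repeat the post-hoc weighting with the common clock as a sensitivity analysis.

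The cost is a few sentences, one derived variable and possibly one re-run. The common-clock version carries post-hoc status. LSN to 911 call also answers a slightly different question from time to arrival, and effect modification by time to MSU arrival can be described only within the MSU arm.

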5.1.6. Missing Data

We expect no missing data for baseline measures. For 90-day assessments, extensive efforts will be made to ascertain the modified Rankin scores and mortality status, though we anticipate a 5% rate of lost to follow-up. We will perform several approaches for handling missing data. Characteristics of patients who are lost to follow-up will be compared to those that remain in the study to assess the degree of any selection bias, and sensitivity analyses will be performed to evaluate robustness of conclusions to the different missing data approaches. We will use multiple imputation for the final values assuming missing at random, depending on if any significant baseline differences exist between those observations that have a missing value or not. As sensitivity analyses we will report the data with and without imputation. Data will also be stratified according to their missing pattern (e.g., early termination, late termination, and follow-up completers) and variables representing these groups will be used as model covariates in adjusted analyses.

5.2. Cost Effectiveness Assessment

5.2.1. Approach and Methods used in Cost Analysis.

In order to establish an economic basis for a higher reimbursement from the healthcare

payers for dispatching an MSU the following aspects have to be established:

- Does the MSU improve the post-discharge stroke severity and consequently improve average patient QALYs? Higher cost for an intervention can be better justified if associated with improved patient outcomes.
- Does the MSU reduce post-stroke healthcare utilization and consequently costs for the healthcare payers? Reduction of post-stroke healthcare utilization will subsequently save costs for the healthcare payers who pay for these utilizations. By identifying whether the healthcare payers save costs for stroke management due to the use of MSU (and determining the amount of post-stroke cost savings) the study can provide scientific evidence for supporting additional Medicare reimbursements for an MSU dispatch.
- What is the magnitude of the incremental fixed costs associated with MSU and the per-patient incremental fixed cost due the ambulance outfitting, CT, other equipment, and telemedicine technology, staffing requirements and paramedic training? Establishing the magnitude of incremental fixed cost per patient will help determine the justifiable amount of increased reimbursements to agencies operating the MSU and providers supporting its telemedicine capabilities.

5.2.2. Sample used for Cost Analysis

The cost-effectiveness analysis (CEA) will include all enrolled patients on MSU and SM weeks who meet criteria for tPA treatment whether or not they are eventually treated with tPA. We estimate that approximately 50% of enrolled patients will receive tPA in the MSU and SM group. The non-tPA treated patients will probably not benefit much from MSU management and since the primary goal of the MSU is to ensure quicker administration of tPA, only those patients who meet criteria to receive tPA will be included in the cost analysis (for one year cost and QALY follow-up). The cost of operating the MSU for the remaining 50% of the patients who are not eligible for tPA administration will be included as fixed costs of operating the MSU, but these patients will not be followed-up once they are deemed ineligible to receive tPA inside the MSU or at the ED.

